5.0 Statistical Measures

5.1 Outcome Measurements

The primary outcome is the cumulative NFkB signal in innate immune cells 1 and 24 hours after surgery.

Secondary outcomes include HMGB1 plasma levels, functional recovery trajectories (measured objectively with ActiGraph and subjectively with WOMAC function sub-scale), postoperative pain resolution (measured with WOMAC-pain subscale), and postoperative resolution of fatigue and resulting impairment of daily activities (measured with SRS). Trajectories will be reflected by the time to resolve function to mild impairment, the time to resolve pain to mild levels, and the time to resolve fatigue to 50% of maximum postoperative fatigue.

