3.3 Enrollment

We plan to enroll 36 participants. All participants will be enrolled at Stanford Health Care.

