4.0 Materials and Methods

The proposed study is designed as a randomized, controlled, and double-blind study comparing a daily dose of cacao flavanol versus placebo. Cocoa flavanol is commercially available as a nutrient (CocoaVia®), manufactured by Mars Inc. CocoaVia® is supplied in 125 mg capsules

containing 15% epicatechin, the active anti-inflammatory ingredient. Based on our preliminary data a daily oral dose of 1,000 mg will be used in this study.

After participants have completed the informed consent process they will be randomized to one of two treatment groups - half to group A and half to group B. Group A participants will receive a daily oral dose of 1,000 mg cocoa flavanol (CocoaVia®) for 5 days before surgery, while group B participants will receive a daily oral dose of a placebo for 5 days before surgery.

Patients will be involved in study procedures from the time they consent to participate through postoperative week 6. Procedures to evaluate baseline condition, hospital course, and recovery will take place as follows:

Questionnaires: Before hospitalization participants will complete questionnaires to evaluate expectations prior to surgery (patient expectations), stress level (perceived stress scale), pain and function (WOMAC), anxiety (POMS-anxiety scale), and baseline fatigue and functional impairment (surgical recovery scale; SRS). Participants will complete SRS and WOMAC scales daily while they are in the hospital, and weekly following discharge to track recovery over a sixweek course.

Objective measures of function: Physical function will also be measured objectively by directly monitoring participant activity using a wearable device (ActiGraph) providing measurements for physical activity/function and sleep. Participants will be asked to wear the device beginning 1 week before surgery through postoperative week 6.

Blood draws: Blood will be drawn at 4 time points; once before administration of the study intervention (40ml), 1 hour before surgery (30ml), 1 hour after surgery (30ml), and on post-op day 1 (30ml). Blood will be processed for analysis of cell signaling with mass cytometry (NFkB in innate immune cells), HMGB1 plasma concentrations, and epicatechin (flavanol) plasma concentrations. Blood samples will be identified using a study code, and will be analyzed in labs at Stanford University and Stanford Health Care (Stanford Hospital).

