5.2 Analysis Plan

Page 6 Protocol Version # 1 The primary outcome NFkB signaling in innate immune cells between the two study groups will be analyzed with a non-paired t-test. A similar exploratory analysis will be conducted for secondary outcomes. However, the study is powered to detect differences of the primary outcome.

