5.3 Sample size

Based on data from previous studies of surgical patients receiving an active (arginine nutritional supplement) versus a control treatment, it is reasonable to assume that intervention-related effect sizes (changes in signaling activity) are about twice as large as pooled standard deviations. This has been noted for signaling molecules downstream of TLR4 in response to arginine supplementation. TLR4-signaling (NFkB) is the primary outcome of this proof-of-concept study. A sample size of 16 patients per group should therefore provide ~80% at p<0.05 to detect an intervention-related group differences.

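### The exploratory recovery analysis ignores the pre-operative score and reduces repeated WOMAC scores to one time to mild; a baseline-adjusted longitudinal model beside it would be a cheap, optional gain in efficiency

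*Combined protocol and SAP*

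**What the plan says.** All references are to the combined protocol and SAP.

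- **Collection (4.0).** WOMAC and SRS are completed once before hospitalization. Afterwards: "Participants will complete SRS and WOMAC scales daily while they are in the hospital, and weekly following discharge to track recovery", over six weeks.
- **Summary (5.1).** For function and pain: "Trajectories will be reflected by the time to resolve function to mild impairment, the time to resolve pain to mild levels". Fatigue on the SRS is likewise reduced to a time, that of falling to half of its post-operative maximum.
- **Test (5.2).** The primary NFkB outcome gets an unpaired t-test. For the rest: "A similar exploratory analysis will be conducted for secondary outcomes". The section adds that the trial is powered for the primary outcome.
- **Size.** 3.3: "We plan to enroll 36 participants"; 4.0: "half to group A and half to group B", hence 18 per group. The power statement in 5.3 uses 16 per group.

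No covariate, repeated-measures model or time-to-event method is named. That the recovery times are compared without adjustment is an inference from the word 'similar'.

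**The concern.** Two kinds of information are collected and then not used. One is the patient's pre-operative level, which is likely to influence when a fixed cut-off is reached. The other is the size of each score: how far above or below mild it lies, and everything after the first crossing.

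Section 1.0 makes preliminary patient-centered recovery data, and their relation to flavanol intake, the secondary aim. With enrolment fixed at 36 for a different endpoint, the analysis is the main place left to gain precision. An uninformative recovery comparison could discourage follow-on work although the collected data could have said more.

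**Working it through.** **The plan's own figure.** The only power figure is for NFkB: "A sample size of 16 patients per group should therefore provide ~80% at p<0.05", with effects that "are about twice as large as pooled standard deviations". By the normal approximation, power = Φ(d√(n/2) − 1.96). With n = 16, d = 2 gives Φ(5.66 − 1.96) = 99.99%, and d = 1 gives Φ(2.83 − 1.96) = 80.7%. The stated 80% therefore does not follow from the stated effect. That is a separate matter for the primary outcome. No figure is given for recovery.

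**Inputs here.** From the documents: 18 per group, one pre-operative score, weekly scores to week 6. Assumed, because the documents give none: two-sided 5%, effect sizes, the correlation ρw between weekly scores, the correlation ρb of the baseline with each score, and the cut-off.

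**Check by hand.** For the mean of r = 6 scores, the variance relative to one unadjusted score is (1 + 5ρw)/6. Baseline adjustment subtracts ρb². Take a middle case, ρw = 0.7 and ρb = 0.5:

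- unadjusted mean: (1 + 3.5)/6 = 0.75
- adjusted mean: 0.75 − 0.25 = 0.50

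With n = 18, √(n/2) = 3. For a constant 0.5 SD shift:

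- one unadjusted score: Φ(1.50 − 1.96) = 32%
- unadjusted mean: Φ(1.50/√0.75 − 1.96) = Φ(−0.23) = 41%
- adjusted mean: Φ(1.50/√0.50 − 1.96) = Φ(0.16) = 56%

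**Simulation.** A crossing time has no such formula, so it was simulated: 6,000 trials per setting, 18 per group, two cut-offs, patients who did not cross set to week 6. Power in %, first / second (stricter) cut-off:

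| Effect | Time, unadjusted | Time, adjusted | Mean, unadjusted | Mean, adjusted |
|---|---|---|---|---|
| Constant 0.5 SD, middle case | 31.2 / 29.4 | 37.9 / 34.1 | 38.8 / 39.5 | 52.5 / 52.8 |
| Constant 0.8 SD, middle case | 64.4 / 62.8 | 75.6 / 72.6 | 76.0 / 76.9 | 89.8 / 90.2 |
| 1.2 SD fading to 0 by week 6 | 65.6 / 47.4 | 76.1 / 55.8 | 53.7 / 52.9 | 68.8 / 68.5 |

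Type I error was near 5% for every method. Under a constant shift the crossing time carries about as much information as one unadjusted score. A log-rank test did about as well as the t-test there (63-64% at 0.8 SD), so censoring unresolved patients properly does not remove the loss.

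**Range for a sustained 0.5 SD shift.**

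- With ρb 0.3-0.7 and ρw 0.5-0.7: 28-34% for time to mild against 41-81% for the adjusted mean.
- A second set of assumed correlations: 32-34% against 51-65%.
- When every simulated patient resolves: 29-30% against 50-65%.
- With no baseline correlation: 33% against 45-46%, so discarding score size costs something by itself.
- With 16 per group, middle case: 26-28% against 46-47%.

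**Other shapes of benefit.**

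- Faster recovery to a common floor: 24-39% for time to mild against 21-64% for the adjusted mean.
- Some early or mid-course benefits: 56-57% against 35-45%, in favour of time to mild.

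**Baseline adjustment alone.** It raised power in every scenario with an effect. For the crossing time the gain is 1.4 to 3.2 points at ρb = 0.3 with ρw = 0.7, and 4.7 to 11.2 points in the middle case.

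**The case against.** **The outcomes are exploratory.** Section 5.2 says so and reserves power for the primary outcome; section 1.0 speaks of preliminary data. This stands, and it settles the severity: no stated conclusion or decision depends on these tests.

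**Time to mild fits the hypothesis.** Section 2.0 expects cocoa flavanols to speed up clinical recovery, and a time answers how much sooner. A six-week mean answers a different question. This stands too, so the time should not be demoted.

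**The gain rests on assumptions.** A constant shift favours a mean. A reader might infer that the crossing time wastes much of the power whatever the benefit looks like. The documents give no WOMAC SD, correlation or effect shape from which to say that, and some plausible shapes reverse the ranking. Part of the gain also comes from baseline adjustment rather than from the repeated scores, and how well a pre-operative arthritis score predicts post-operative scores is unknown here.

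**The unadjusted test is inferred.** True. 'Similar' to an unpaired t-test is most naturally read that way, but a sentence in 5.2 would settle it.

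**Conclusion.** The concern holds in a limited form. The plan makes no stated use of the pre-operative score in comparing recovery, and adjusting for it helped in every scenario with an effect, though only slightly when the correlation is weak. Reducing the series to a crossing time costs further power if the benefit is a sustained shift: about 32-34% against 51-65% at 0.5 SD with 18 per group. For early, mid-course or faster-to-the-same-level benefits the advantage can be nil or reversed.

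All these figures rest on assumed WOMAC correlations and effects and on complete questionnaires. The longitudinal model proposed below was not itself simulated; the adjusted six-week mean stands in for it.

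Two stronger readings are not supported. The planned test is not invalid: its type I error is near 5%, given a rule for patients who do not reach mild. Nor would the change make the trial adequately powered for recovery: at 0.5 SD the middle case reaches only about 53%. This is an optional efficiency improvement.

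**What to change.** In section 5.2:

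1. Keep time to mild for WOMAC pain and function as a stated recovery outcome, and adjust its comparison for the pre-operative score of that subscale.
2. Beside it, pre-specify for each subscale a longitudinal model of the post-operative scores to week 6. Time runs from surgery, not from discharge, because discharge comes after randomization and could be affected by treatment. Terms: time (categorical or flexible), arm, arm-by-time, pre-operative score and a patient random effect. Report the arm difference averaged over weeks 1-6 with its 95% interval.
3. Treat SRS fatigue the same way, using its pre-operative score.
4. Label both analyses exploratory.

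The cost is a few sentences and one standard model, with no new data or visits. The downside is one additional exploratory result per scale, in score points rather than days. The two results may differ, since they answer different questions, so the plan should say that both will be reported.

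### The only named fatigue summary measures relative speed; if it uses each patient's own maximum it cannot show a proportional fall in severity, so an SRS area should stand beside it, with a stated rule for unresolved patients

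*Combined protocol and SAP*

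**What the plan says.** Section 5.1 lists among the secondary outcomes "postoperative resolution of fatigue and resulting impairment of daily activities (measured with SRS"), and then reduces each recovery trajectory to a time. Function and pain are timed to a mild level, which is a fixed threshold. Fatigue alone has a relative threshold: "the time to resolve fatigue to 50% of maximum postoperative fatigue". Whose maximum this is, the patient's own or the scale's, is not stated. No section names an SRS mean, peak or area.

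Section 4.0 sets the schedule: "Participants will complete SRS and WOMAC scales daily while they are in the hospital, and weekly following discharge". It also sets the end of follow-up: "Patients will be involved in study procedures from the time they consent to participate through postoperative week 6". A pre-operative SRS score is planned and described as baseline, but it is placed only before hospitalisation, not before the first dose.

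In Section 5.2 the primary outcome "will be analyzed with a non-paired t-test", and "A similar exploratory analysis will be conducted for secondary outcomes". Nothing says how a patient who has not reached a threshold by week 6, or who stops reporting, enters that analysis. Section 3.3 states "We plan to enroll 36 participants", and Section 4.0 allocates half to each group, so 18 per arm.

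**The concern.** On the most natural reading, the maximum is the patient's own highest score after surgery. That score is measured after randomisation and dosing, so treatment can change the yardstick as well as the recovery. A null or adverse result on the 50% time could then mean no benefit, or milder fatigue that declines at the same relative pace, and no planned SRS summary would separate the two. For a proof-of-concept trial that gathers preliminary patient-centred data, this bears on which outcome a later trial should use.

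A second gap concerns all three time outcomes. Follow-up stops at week 6, so some patients may have no observed time to mild function, mild pain or halved fatigue, and the plan has no rule for them.

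**Working it through.** The plan gives no figure for any fatigue outcome; its one power statement (Section 5.3) concerns NFkB. The check is therefore algebra, followed by illustration under assumed values.

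**1. Invariance.** If F(t) becomes c·F(t), the patient's maximum is multiplied by c too, and the time at which the score reaches half of it does not move. This needs the patient's own maximum and a score on which higher is worse and zero means no fatigue.

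**2. Curves.** Assume F(t) = B + (P − B)·2^(−t/h), with peak P, floor B and half-life h in days. With r = B/P:

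- 50% time = h·log2[(1 − r)/(0.5 − r)], undefined for r ≥ 0.5
- Area to day 42 = 42B + (P − B)·(h/ln 2)·(1 − 2^(−42/h))

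Placebo with P = 80, B = 20, h = 10 has r = 0.25. Its time is 10·log2(0.75/0.25) = 15.8 days and its area is 840 + 60·13.642 = 1659.

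| Active differs by | 50% time, placebo vs active (days) | Area, placebo vs active |
|---|---|---|
| Whole curve × 0.75 (P 60, B 15) | 15.8 vs 15.8 | 1659 vs 1244 |
| Half-life 7 | 15.8 vs 11.1 | 1659 vs 1436 |
| Peak 60, floor 20 in both | 15.8 vs 20.0 | 1659 vs 1386 |
| Peak 60, floor 10 in both | 12.2 vs 13.2 | 1375 vs 1102 |
| Peak 60, floor 0 in both | 10.0 vs 10.0 | 1091 vs 819 |

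The 50% time picks up speed. It misses a proportional fall, and it reverses only when the peak falls over a non-zero floor. The third row cuts the rise above the floor from 60 to 40, that is, by one third.

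**3. Unresolved at day 42.** This happens if h > 42/log2[(1 − r)/(0.5 − r)]: 42 days at r = 0, 26.5 at 0.25, 16.2 at 0.40, 12.1 at 0.45, and always for r ≥ 0.5.

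**4. Simulation.** 18 per arm; visits on days 1, 2, 3, 7 and then weekly to 42; scores limited to 0-100; two-sided 5%; 4,000 trials per scenario, with repeat runs of 1,500. Area was compared by a linear model on arm and pre-operative score. All settings are assumed:

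| Setting | Floor, mean (SD) | Rise, mean (SD) | Half-life median (log-SD) | Score and pre-operative noise SD |
|---|---|---|---|---|
| A | 20 (8) | 60 (10) | 10 (0.35) | 5 |
| B | 20 (12) | 60 (18) | 10 (0.5) | 10 |
| C | 30 (10) | 50 (12) | 14 (0.5) | 6 |

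Results for A/B/C:

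| Scenario | Log-rank on 50% time | Adjusted area |
|---|---|---|
| No effect | 5.6/5.3/5.6% | 5.5/5.1/5.0% |
| Rise cut by one third | against active 18/4/15% (repeat 18/3/13%) | for active 72/36/59% (about 72/34/56% in a repeat) |
| Half-life 30% shorter | 42/18/22% | 50/23/30% |
| Whole curve 25% lower | for active 5/9/9% | for active 98/73/98% |

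In the last row the log-rank rates are not exactly null, because the noise and the 0-100 limits do not scale with the curve. Placebo patients unresolved at week 6 were 2/4/29%. For the cut in rise, baseline adjustment raised area power in A from 46% to 72%; with a zero floor it added nothing (73% vs 72%).

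A separate simulation with a zero floor, a 14-day half-life and wider spread gave, for severity 30% lower, 5.7% for log-rank and 48% for log area. For a halved half-life it gave 86% and 76%, so area is not always the stronger summary.

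**5. Unresolved patients.** Setting C with half-life halved: a t-test with unresolved patients set to day 42 finds the effect in 59-61% of trials, log-rank in 53-56%, and a t-test on observed times only in 39-40%. With 15% dropout assumed, log-rank is at 52% and the day-42 t-test at 49%.

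**The case against.** The plan chose speed: the outcome is labelled as resolution, and Section 2.0 hypothesises faster recovery. A speed measure ignores level by definition, and no section claims an effect on peak fatigue. This stands as a defence of keeping the 50% time. It does not supply a severity summary, which the SRS data could give at no extra burden.

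The severity point also depends on a reading. If the scale maximum is meant, the threshold is a common level and the point falls away. That stands, and it is why the plan should say which maximum applies.

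Four stronger readings are tempting, and the documents do not support them:

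- A reader might infer that the planned t-test discards unresolved patients. Section 5.2 does not say so. The log-rank gain in step 5 appears against dropping them; against a day-42 rule the t-test is slightly ahead unless there is dropout.
- A reader might take 98/73/98% as the power of the area. That scenario has five days of dosing hold the pre-operative floor 25% lower through week 6. A fall in the surgical rise alone is more plausible.
- A reader might expect the reversal. It needs an own maximum, a lower peak, a non-zero floor and an unchanged half-life, and it nearly vanishes in setting B.
- A reader might treat the week-6 limit as a fatigue problem. It applies equally to function and pain.

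**Conclusion.** The point holds as a minor one. The 50% time is a valid randomised comparison of relative speed, and false positives are not inflated (5.3-5.6% under no effect). If each patient's own maximum is meant, it is blind to a proportional fall in severity, and it can lengthen on active when the peak falls over an unchanged non-zero floor. The blindness follows by algebra; every size above rests on assumed curves, because SRS range, direction and values are not given. The missing rule for unresolved and lost patients is a real gap across all three time outcomes. The case for a log-rank test is valid handling of those patients, not a general power advantage. These outcomes are exploratory and unpowered.

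**What to change.** In Section 5.1, keep the 50% time and state whose maximum is meant, together with the direction and range of the SRS. Before unblinding, add SRS area under the curve to week 6 as an exploratory outcome, time-weighted for the daily-then-weekly schedule, with a rule for missed scores. Compare arms with adjustment for the pre-operative SRS score if that score is taken before the first dose; otherwise compare without adjustment.

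In Section 5.2, for time to mild function, time to mild pain and the fatigue 50% time, treat patients unresolved at week 6 or lost earlier as censored, and use a log-rank test in place of the t-test.

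The cost is a few sentences, with no new data and no change in sample size. There is one more exploratory result to report. Area mixes peak height with speed, so it must be read beside the 50% time. Weekly visits still leave the times coarse, with many ties.

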5.2 Analysis Plan

Page 6 Protocol Version # 1 The primary outcome NFkB signaling in innate immune cells between the two study groups will be analyzed with a non-paired t-test. A similar exploratory analysis will be conducted for secondary outcomes. However, the study is powered to detect differences of the primary outcome.

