1.0 Specific Aims and Major Rational

The primary aim of this mechanistic, double-blind, placebo-controlled proof-of-concept clinical trial is to demonstrate that preemptive oral administration of cocoa flavanol for five days before surgery (equivalent to 50 grams of dark chocolate per day) will attenuate the surgery-evoked increase of HMGB1 in blood plasma and NFkB signaling in innate immune cells shortly after surgery. The HMGB1-NFkB signaling axis is a major pro-inflammatory axis that is activated in response to tissue trauma. Preemptive attenuation of this axis in multiple animal injury models is associated with reduced tissue damage and increased survival. A secondary aim is to capture preliminary patient-centered outcomes data including postsurgical pain and daily functioning for six weeks after surgery, and relate these outcomes to the intake of oral cocoa flavanol and surgery-evoked activation of the HMGB1-NFkB signaling axis.

The protocol for this trial is embedded in previous studies by Drs. [name] and [name] that examined immune correlates of surgical recovery in patients undergoing major joint replacements.^{1,2} These studies have demonstrated that exaggerated activation of NFkB-signaling in innate immune cells in response to surgery predicts delayed resolution of pain and delayed functional recovery after surgery.

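### The primary t-test gives no stated role to the pre-intervention NFkB sample; adjusting for it by ANCOVA would gain precision if it correlates with the outcome above about 0.2

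*Combined protocol and SAP*

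**What the plan says.** Section 5.1 defines the endpoint: "The primary outcome is the cumulative NFkB signal in innate immune cells 1 and 24 hours after surgery". It does not say how the two time points are combined. Section 5.2 gives the whole primary analysis in one sentence: "The primary outcome NFkB signaling in innate immune cells between the two study groups will be analyzed with a non-paired t-test". Neither section mentions a covariate, a change score or a baseline.

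Section 4.0 lists four blood draws: "once before administration of the study intervention (40ml), 1 hour before surgery (30ml), 1 hour after surgery (30ml), and on post-op day 1 (30ml". The sentence on assays covers the blood as a whole: "Blood will be processed for analysis of cell signaling with mass cytometry (NFkB in innate immune cells), HMGB1 plasma concentrations, and epicatechin (flavanol". This implies, without stating it, that NFkB is measured in the first draw.

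Two other places hint at a change from a pre-operative value. The aim in Section 1.0 is that the intervention "will attenuate the surgery-evoked increase of HMGB1 in blood plasma and NFkB signaling in innate immune cells shortly after surgery". Section 5.3 assumes that "intervention-related effect sizes (changes in signaling activity) are about twice as large as pooled standard deviations". Neither says which sample would be the reference or how it would enter the test.

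**The concern.** Read plainly, the outcome is made up of post-operative values only. A measure of the same variable, taken before any study product, then appears to be collected but not used in the primary comparison. In a trial this small, adjusting for such a value is a standard way to reduce residual variance.

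If the sponsor instead intends a change score, the pre-operative value is used, but usually less efficiently than in ANCOVA. The text should settle which is meant before data are seen.

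What is at stake is the width of the interval and the power. The type I error and the unbiasedness of the estimate are not in question.

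**Working it through.** **Inputs from the documents.** Section 5.3: 16 per group, about 80% power, p<0.05, effect about 2 pooled SDs. Section 3.3: 36 enrolled, so 18 per arm at most. Section 4.0: equal allocation.

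**Assumptions.** Two-sided 5% test; rho from 0 to 0.7; normal data with a common slope in both arms.

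**The plan's own figure.** For the t-test with n per arm and standardised effect d, the noncentrality is d × √(n/2) on 2n − 2 degrees of freedom.
- d = 2, n = 16: 2 × √8 = 5.66 on 30 df, power 99.98%. The stated figure of about 80% does not reproduce.
- d = 1, n = 16: √8 = 2.83 on 30 df, power 78.1% (80.7% by normal approximation). This is the effect size that matches the stated power, so it is used for the comparison below.

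**Break-even.** For one normal covariate and N patients in total,

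Var(ANCOVA) / Var(t-test) = (1 − rho²) × (1 + 1/(N − 4)).

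The second factor is the cost of estimating the slope.
- N = 32: factor 29/28 = 1.036, so break-even is rho = √(1/29) = 0.186 (0.190 when the lost degree of freedom is counted as well).
- N = 36: factor 33/32 = 1.031, so break-even is rho = √(1/33) = 0.174.

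**Power and interval width, post-operative outcome, 16 per arm, d = 1.** ANCOVA uses 2n − 3 = 29 df, with power averaged over the chance covariate imbalance. The t-test has power 78.1%, an effect detectable with 80% power of 1.02 SD, and a mean 95% CI half-width of 0.716 SD.

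| rho | ANCOVA power | Detectable effect, SD | CI half-width, SD | Width vs t-test |
|---|---|---|---|---|
| 0 | 76.7% | 1.04 | 0.729 | 2% wider |
| 0.2 | 78.3% | 1.02 | 0.715 | unchanged |
| 0.3 | 80.4% | 0.995 | 0.696 | 3% narrower |
| 0.5 | 87.3% | 0.90 | 0.632 | 12% narrower |
| 0.7 | 96.4% | 0.745 | 0.521 | 27% narrower |

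A simulation with 200,000 replicates agreed on power, with type I error of 0.049 to 0.050 and bias of at most 0.001 in absolute value. With 18 per arm, t-test power is 83.0% and ANCOVA power is 81.8%, 83.3%, 85.2%, 91.1% and 98.0% at the same values of rho.

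**Chance imbalance.** The SD of the baseline difference is √(2/n): 0.354 at n = 16 and 0.333 at n = 18. A difference above 0.5 SD in either direction is then 1.41 or 1.50 standard errors, with probability 15.7% or 13.4%. Such a difference moves the unadjusted estimate by rho × 0.5 SD: 0.15, 0.25 and 0.35 SD at rho 0.3, 0.5 and 0.7.

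**Change-score reading (from the first draw, equal SDs assumed).** The variance ratio to the post-operative t-test is 2(1 − rho). Power is 49%, 58%, 64%, 78% and 94% at rho 0, 0.2, 0.3, 0.5 and 0.7. The ANCOVA interval is 28%, 21%, 18%, 12% and 6% narrower. Setting 2(1 − rho) = (1 − rho²) × 29/28 gives break-even at rho = 56/29 − 1 = 0.93.

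**Missing baselines (one per arm).** Dropping those patients gives ANCOVA power of 73.7%, 75.4%, 77.6%, 84.8% and 95.2%, and moves break-even to rho 0.32. Replacing the missing covariate with the pooled mean gives 76.6%, 78.1%, 80.2%, 86.5% and 95.3%, with type I error of 0.049 to 0.050.

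**The case against.** The strongest objection is that nothing in the plan is wrong. A t-test is a standard prespecified analysis for a proof-of-concept trial. No passage reports how NFkB before five days of dosing relates to NFkB after surgery, and below rho of about 0.2 the proposal slightly widens the interval. That stands, and it is why the point is graded as an optional improvement.

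The power gain also appears only at 1 SD, whereas Section 5.3 assumes 2 SD, where t-test power is already 99.98%. This stands too: at 2 SD the benefit is interval width alone. But the power stated in Section 5.3 corresponds to about 1 SD, so the larger effect is not a safe basis for planning.

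The change-score figures rest on equal SDs. If the outcome is the sum of two values and one baseline is subtracted, with equal single-time SDs and a correlation of 0.3 to 0.8 between the 1 h and 24 h values (an assumption), the change-score variance ratio at rho 0.5 is about 0.75 to 0.76, against 0.78 for ANCOVA. If a baseline is subtracted from each value, the change score does worse than in the equal-SD case (power 67% to 76% at rho 0.5). So the 0.93 break-even is not general. The comparison with the post-operative t-test is unaffected.

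Finally, chance imbalance is already reflected in the t-test's standard error. It is another view of the same loss of precision and should not be counted twice.

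**Conclusion.** The concern holds as a conditional, optional improvement. As written, the primary test assigns no role to a pre-intervention sample that probably includes the outcome measure. ANCOVA on that value beats the post-operative t-test once rho exceeds about 0.17 to 0.19. The gain is negligible at 0.2, small at 0.3 and material from 0.5, where power at 1 SD rises by 87.3 − 78.1 = 9.2 points. The worst case, rho 0, costs about 1.5 points of power.

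Confidence is medium. The size rests on an unreported rho and an assumed 1 SD effect. The cost rests on NFkB being assayed in the first draw, which is implied but not stated.

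**What to change.** - **Section 5.1:** define the cumulative signal, for example as the sum of the 1 h and 24 h values. State whether it is a post-operative value or a change from a named sample.
- **Section 5.2:** make the primary analysis an ANCOVA of that outcome on treatment group and the first-draw NFkB value, two-sided 5%. Keep the unadjusted t-test as a sensitivity analysis.
- **Section 4.0:** state that NFkB is assayed in the first draw.
- **Missing baselines:** retain the patient and set the covariate to the mean of all observed baselines, both arms pooled.
- **Choice of covariate:** do not use the sample taken 1 hour before surgery, because it follows five days of dosing. If a change from that sample is intended, label it as a different estimand: it leaves out any treatment effect already present before surgery.

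The cost is one degree of freedom and a few lines of text if the first-draw assay is already planned. Otherwise it needs up to 36 further mass cytometry assays on blood already drawn. If rho is near 0, the interval is about 2% wider.

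### The primary outcome needs both post-operative samples but is tested with an unadjusted t-test, so one missing sample removes the patient by default and the pre-dose value goes unused

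*Combined protocol and SAP*

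**What the plan says.** Section 5.1 defines the primary outcome as the "cumulative NFkB signal in innate immune cells 1 and 24 hours after surgery". How the two times are combined (sum, mean or area under the curve) is not stated. Section 4.0 lists four draws: one before the first dose, one shortly before surgery, and the two that feed the outcome, "1 hour after surgery (30ml), and on post-op day 1 (30ml"). It sends the blood for mass cytometry, so a pre-dose NFkB value should exist for each patient.

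Section 5.2 gives the whole primary analysis in one sentence: the outcome "will be analyzed with a non-paired t-test". The document states no covariate, analysis set, rule for a missing or unusable sample, or sensitivity analysis. It also does not say what happens to the day-1 draw if a patient has already gone home.

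On size, section 5.3 assumes effects that "are about twice as large as pooled standard deviations". It says that 16 per group "should therefore provide ~80% at p<0.05 to detect an intervention-related group differences". Section 3.3 says "We plan to enroll 36 participants", with no reason given for the four beyond 32.

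**The concern.** A score built from two samples does not exist when one is absent, and a two-sample t-test cannot use the one that remains. Unless a rule is added, the plan therefore leads to a complete-case analysis. With 36 patients, each one lost is about 3% of the data (1/36), and a valid 1-hour measurement may be discarded with the patient.

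Two things are at stake. The first is precision: patients drop out of the only powered test, and a baseline covariate that could reduce residual variance is ignored. The second is possible bias. Sections 1.0 and 2.0 link stronger NFkB/TLR4 signalling to slower recovery, and the hypothesis is that the intervention lowers signalling. If low-signal patients were more likely to miss the day-1 sample, more of them would be missing from the active arm whenever the intervention works. The patients left would then look more alike across arms.

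**Working it through.** **The plan's own power figure.** Inputs from section 5.3 are 16 per group, p<0.05 (two-sided assumed) and a difference of 2 SD. For a two-sample t-test the noncentrality is d × √(n/2), with 2n − 2 degrees of freedom.

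- d = 2, n = 16: 2 × √8 = 5.66, power 99.98%. At d = 2, 80% power needs only 6 per group.
- d = 1, n = 16: 2.83, power 78.1% (80.7% by normal approximation).
- Solving for 80% at n = 16 gives d = 1.02.

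The stated ~80% is therefore not reproduced at 2 SD. It fits an effect near 1 SD. That inconsistency is a separate matter; here results are shown at both effects.

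**Loss at random.** The rate is an assumption: each of the two draws is missed independently with probability q. The share with both samples is (1 − q)². Starting from the 18 per arm enrolled:

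| q per draw | Both samples | Per arm | Power, d = 1.02 | Power, d = 2 |
|---|---|---|---|---|
| 0 | 100% | 18 | 84.6% | >99% |
| 5% | 90.25% | 16.2 | 80.5% | >99% |
| 10% | 81% | 14.6 | 75.8% | >99% |

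The surplus over 32 absorbs (36 − 32)/36 = 11.1% incomplete pairs. By contrast, the share with at least one sample is 1 − q², or 99.75% and 99%. An analysis that uses partial data keeps nearly everyone.

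**Loss related to signal.** All inputs except the 18 per arm are assumptions. The simulation has correlation 0.5 between times, a true difference of 1.02 SD in the combined value, and day-1 loss more likely when the 1-hour value is low. The likelihood estimate uses the 1-hour value of patients without a day-1 sample.

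| Lost, placebo / active | Complete-case difference (SE) | Complete-case power | Likelihood estimate (SE) |
|---|---|---|---|
| none | 1.02 (0.33) | 84% | – |
| 10% / 19% | 0.95 (0.35) | 75% | 1.02 (0.34) |
| about 20% / 36% | 0.93 (0.38) | about 65% | 1.03 (0.35) |

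Repeat simulations move the differences by about 0.01.

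That set-up is missing-at-random by construction and so favours the likelihood method. Making loss depend on the unseen day-1 value at similar rates gives about 0.93-0.95 for complete case and 0.97-0.99 for likelihood. The likelihood estimate is then biased too, but less, and its SE is again smaller.

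**Range under a stronger mechanism.** Here loss depends directly on the combined value and the true difference is 1 SD. With 10% overall loss and a logistic slope of 1 per SD, the complete-case difference is 0.93 SD and power 77%. With 30% loss and a slope of 2 it is 0.71 SD and 50%, but that requires about 43% of the active arm to lose the sample. At a true 2 SD, power is at least 96% in every case run. With no true effect there is no bias, and the type I error stays about 5%.

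**Pre-dose adjustment.** If r is the within-arm correlation of pre-dose NFkB with the outcome, adjustment multiplies the residual variance by about 1 − r². The documents give no r, so no gain is claimed in figures.

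**The case against.** The strongest reply is that nothing in the documents shows the day-1 sample will be lost. A reader might infer that fast recoverers go home before the draw and that the comparison is therefore biased toward no effect. The documents do not support this. They give no length of stay and no early-discharge rate; section 4.0 plans a day-1 draw and daily in-hospital scales, which presupposes a stay. The cited link is between NFkB and recovery of pain and function, not discharge within a day. The bias needs unsampled patients, loss related to signal, and a true effect, all together. This part of the reply stands.

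A reader might also deduct losses from 16 per arm and conclude that power falls to 70-75%. That is the wrong start: 18 per arm are planned, and at 5% per draw the ~80% is kept. The purpose of the surplus is not stated, but it is there. Nor is 1.02 SD the protocol's figure; it is solved back from 16 per group and ~80%. At the stated 2 SD the power loss is negligible.

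Finally, exclusion of incomplete patients is inferred from silence, not written as a rule. This is true, but it does not answer the point: the stated test has no other way to treat a patient without a combined value. A statistician would have to improvise one after seeing which samples failed.

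**Conclusion.** The concern holds in a limited form. As written, the primary analysis by default drops any patient lacking either post-operative sample and leaves the pre-dose value unused, although a better method is available for data the trial already plans to collect.

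The likely cost is modest. At an effect near 1 SD, random loss of 5-10% per draw gives power of about 80-76%; at 2 SD power remains above 99%. Signal-related loss could pull a true 1.02 SD difference to about 0.95-0.93 SD at the main rates tried, a shift of 0.07-0.09 SD against a standard error of about 0.35-0.38. Loss rates, the correlation and the missingness mechanism are all assumptions. If loss is unrelated to NFkB, or there is no true effect, the estimate is not biased.

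**What to change.** Amend section 5.2 before unblinding:

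- Make the primary analysis a repeated-measures mixed model of the 1-hour and day-1 NFkB values with arm, time, arm-by-time and pre-dose NFkB, unstructured covariance and small-sample degrees of freedom.
- Include every randomised, operated patient with at least one post-operative value. State how a missing pre-dose value is handled, since a missing covariate would also remove the patient.
- Define the combined outcome in section 5.1, for example as the sum or mean of the two times, and make the primary contrast the arm difference in that combination. If an area under the curve is meant, weight the contrast to match.
- Keep the complete-case t-test as a sensitivity analysis, and add one in which day-1 loss depends on the unobserved value.

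The cost is protocol wording and slightly more analysis work, with no new data. The limit is that the model relies on missing-at-random given the observed values. This is weaker than what the complete-case t-test needs, but it reduces rather than removes bias if loss depends on the unseen day-1 value.
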